7.2 Investigational Agent – Umbralisib

Umbralisib is available as tablets with the following description: 200 mg: Light green, oval tablets with “L474” debossed on one side and plain on the other side.

Umbralisib should be stored at temperatures between 20°C and 25°C (excursions permitted between 15°C and 30°C). Do not freeze. Based on the results available to date, a shelf life of 36 months is proposed for the drug product in the current packaging. Retest dates will be provided periodically by TG Therapeutics, Inc.

7.3 Availability

Ublituximab and umbralisib are investigational agents supplied to investigators by TG Therapeutics Incorporated (TGTX).

7.4 Investigational Agent Ordering

Ublituximab and umbralisib are available from TG Therapeutics. Please allow 5 to 7 business days between drug ordering and drug arrival. Order ublituximab Monday through Wednesday to ensure shipment does not arrive on a weekend day. Ensure staff will be available to unpack

shipment immediately upon arrival. Please direct drug orders to [contact]. The email should include the following:

- Requested quantity of TG Therapeutics study drug(s)
- Date needed
- Principal Investigator name
- Study title
- TG Therapeutics, Inc. tracking number (U2-NTG-004)
- Investigational drug pharmacy shipping address

7.5 Investigational Agent Accountability

Ublituximab and Umbralisib Inventory Records – The investigator, or a responsible party designated by the investigator, in this case the investigational pharmacy of Weill Cornell, will maintain a careful record of the inventory and disposition of all agents received from TGTx on a Drug Accountability Record Form (DARF). If there is any abnormality in the supplied boxes (ublituximab) or bottles (umbralisib), this should be documented during the acknowledgement of receipt and TG Therapeutics should be contacted at [contact].

8. Correlative/Special Studies

Specific correlative studies are not planned with this protocol. However, specimens from subjects will be collected at prespecified time points as outlined in Section 5.1. These specimens will be processed and banked for potential use in future assays. Specimens will be processed and isolated for plasma and mononuclear layer buffy coats for later B and or T cell selection. Genetic analyses may be performed on isolated components. Any and all correlative analyses, including from specimens stored for future research, require written approval by TG Therapeutics, Inc. prior to initiation of the correlative analyses. Investigators and institution may not provide samples taken from subjects to anyone outside of their institution for any purpose without written pre-approval by TG Therapeutics, Inc.

9. Measurement of Effect

9.1. Response Criteria

All response criteria will be assessed using the International Workshop on CLL 2018 guidelines.

9.1.1 Complete Response

Requires all of the following:

- 1) Absence of clonal lymphocytes in the peripheral blood.
- 2) Absence of significant lymphadenopathy. (eg, lymph nodes > 1.5 cm in diameter) by physical examination. In clinical trials, a CT scan of the abdomen, pelvis, and thorax is desirable if previously abnormal. Lymph nodes should not be larger than 1.5 cm in diameter.
- 3) No hepatomegaly or splenomegaly by physical examination. In clinical trials, a

CT scan of the abdomen should be performed at response assessment if found to be abnormal before therapy or if physical examination is inconclusive at the time of evaluation.

- 4) Absence of constitutional symptoms.
- 5) Blood counts above the following values.
 - i) Polymorphonuclear leukocytes $1.5 \times 10^9/L$ (1500/ μL) or more.
 - ii) Platelets more than $100 \times 10^9/L$ (100 000/ μL).
 - iii) Hemoglobin more than 110 g/L (11.0 g/dL; untransfused).

9.1.3 Progressive Disease

Progressive disease is characterized by at least one of the following:

- 1) Appearance of any new lesion such as an enlarged lymph node $>1.5\text{cm}$, splenomegaly, hepatomegaly, or other organ infiltrate.
- 2) An increase by 50% or more in the greatest determined diameter of any previous site.

- 3) An increase of 50% or more in the sum of the product of diameters of multiple nodes.
- 4) An increase in the liver or spleen by 50% or more de novo appearance of hepatomegaly or splenomegaly.
- 5) An increase in the number of blood lymphocytes by 50% or more with at least 5000 B lymphocytes per microliter.
 - i) During umbralisib therapy a lymphocytosis may be seen. any lymphocytosis that occurs in the setting without establishing a nadir or in during a concurrent illness will not be counted as a progression
- 6) Transformation to a more aggressive histology
- 7) Occurrence of cytopenia attributable to CLL. During therapy cytopenias cannot be used to define disease progression.

9.1.4 Stable Disease

Any subject who has not achieved a CR or a PR and do not demonstrate progressive disease, will be considered to have stable disease.

9.2. Duration of response

Duration of response is defined as the interval between the first objective response to the first of disease progression

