5.2. Treatment Administration

All treatment will be administered on an outpatient basis. See section 5.2.1 and 5.2.2 for special precautions relevant for each specific study agent administration. All therapy will be administered in cycles with each cycle consisting of 28 days.

Enrolled subjects will initiate umbralisib monotherapy for a one cycle lead-in defined by Cycle -1. This cycle is designed to allow for correlative assay sample collection to assess early clonal shifts after umbralisib therapy. Without the lead-in these shifts may otherwise be masked by peripheral elimination of circulating tumor cells by anti-CD20 therapy. Subjects will be monitored closely upon initiation with a C-1D15 visit to assess tolerability of umbralisib monotherapy. Upon completion of Cycle -1 subjects will then continue on daily umbralisib and initiate combination therapy with ublituximab (U2). Ublituximab administration and induction/continuation is defined in Section 5.2.1. Ublituximab will only be administered through Cycle 6 (i.e no maintenance administration). Starting at C7D1 enrolled subjects will continue on umbralisib monotherapy. Umbralisib will be given on a continuous once daily basis starting at Cycle -1 for each 28 cycle until disease progression, discontinuation due to toxicity, subject death, subject withdrawal of consent, or investigator withdrawal. Administration schedule and timing of umbralisib administration in relation to ublituximab are further defined in Section 5.2.3. The overall treatment administration is depicted in the schema below Figure 1.

Subjects will be evaluated for objective response after completion of 6 cycles of combination therapy. Subjects with a response \geq PR will be allowed to continue on study (umbralisib monotherapy maintenance). A subject that does not meet objective response criteria by IwCLL 2018 guidelines outlined in Section 9.1 at C7D1 must be taken off study. See section 5.4.1 for further details in management of these subjects not meeting strict response criteria after completion of combination therapy.

Figure 1. Study Drug Administration Schema

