5.5 Duration of Follow Up

The anticipated duration of patients on study therapy will be 2 years though patients deriving benefit will be allowed to continue on study beyond two years. Patients removed from study for unacceptable adverse events will be followed until resolution or stabilization of the adverse event even if that period is longer than 30 days after removal.

After withdrawal from protocol treatment, all patients should be followed for AEs for 30 calendar days after their last dose of either study drug. All new AEs occurring during this period

must be recorded and followed until resolution, unless, in the opinion of the investigator, these values are not likely to improve because of the underlying disease.

Subjects who discontinue study treatment for reasons other than disease progression or withdrawal of consent will be followed for progression free survival and survival every 3 months until documentation of disease progression, death or initiation of CLL directed non study treatment.

Visits for subjects with early treatment discontinuation other than disease progression, death or withdrawal of consent, will continue for 3 months after study drug discontinuation. Subjects and study team should collect the following data during this follow-up period:

- ECOG
- Medical history
- Physical exam
- Vital Signs
- Weight
- CBC with differential
- CMP
- CT neck, chest, abdomen and pelvis with contrast every 12 months or as clinically warranted to document disease progression

Subjects who discontinue therapy for any reason except withdrawal of consent will be followed for overall survival for up to 5 years. Survival follow-up will be documented by either chart review if the subject remains an active patient in the investigators clinic or by phone call every 6 months up to 5 years. If subject is not in active follow-up then a chart note should be placed within the patient chart to confirm survival status.

When the first subject enters year five of treatment or follow-up the study may be amended to address continuation of study therapy or follow-up beyond year 5.

6. Dosing Delays/Dose Modifications

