9.3. Progression-Free Survival

Progression-free survival is defined as the interval between the first treatment day to the first sign of disease progression or death.

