11.1 Study Design/Endpoints

In this single center Phase II study we will evaluate the efficacy and safety of umbralisib and ublituximab (U2) as salvage in patients with CLL who have progressed either on a BTK inhibitor or BCL-2 inhibitor. The study will enroll in two parallel cohorts and subjects will be assigned to cohorts based on the previous novel agent containing regimen regardless of how the novel agents were sequenced, **Cohort A** will consist of patients who progress on BTKi containing regimens and **Cohort B** will consist of patients who progress on BCL-2 containing regimens. Subjects who progress on a regimen containing both a BTKi and a BCL-2 inhibitor, will be enrolled in cohort B. Each cohort will be evaluated independently of each other.

Currently available retrospective evidence demonstrates an ORR of ~35-40% when idelalisib is used as first salvage after ibrutinib failure [11]. Given umbralisib's unique molecular properties and combination therapy with ublituximab, we hypothesize a response rate of 55% using U2 as first salvage. Salvage rates with novel agents after venetoclax failure in subjects considered double refractory are unknown. We anticipate close to 90% of patients enrolled in cohort B will have double refractory disease and represent a high risk group. Given these limitations, we anticipate a response rate of 40% in this group based off the efficacy seen with idelalisib after ibrutinib failure.

Because this is a pilot study, no formal sample size/power calculation is required. Given the anticipated different patient populations in each cohort, no cross cohort comparisons will be performed.

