11.2.2 Analysis of Secondary and Exploratory Endpoints

Analysis of outcomes will remain descriptive. With 12 patients enrolled in Cohort A, an exact binomial (Clopper-Pearson) 95% confidence interval for the CR rate can be constructed to have a width of approximately 46.3% (2.1%, 48.4%). This calculation assumes that the CR rate will approach 16.7% in cohort A. Similarly with 12 patients enrolled in cohort B, and exact binomial (Clopper-Pearson) 95% confidence interval for the CR rate can be constructed to have a width of approximately 38.5% (0.2%, 38.5%). This calculation assumes the CR rate will approach 8% in cohort B. Assuming adequate follow-up time, Kaplan-Meier survival analysis will be used to assess DoR, PFS, and OS, in the entire cohort. All p-values will be two-sided with statistical significance evaluated at the 0.05 alpha level. Ninety-five percent confidence intervals for median DoR/PFS/OS-time and DoR/PFS/OS proportions, will be calculated to assess the precision of the obtained estimates. Safety will be collected and adverse events will be tabulated per incidence of specific AE terms will be reported for the entire cohort. All analyses will be performed in SAS Version 9.4 (SAS Institute, Inc., Cary, NC) and Stata Version 15.0 (StataCorp, College Station, TX).

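### Duration of response ends at progression only, while PFS ends at progression or death, so a responder's death without progression is censored in the planned Kaplan-Meier analysis

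*Combined protocol and SAP*

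**What the plan says.** DoR is a secondary objective (Section 1.2); PFS and overall survival are exploratory (Section 1.3). The definitions differ in their end event:

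- Section 9.2, DoR: "Duration of response is defined as the interval between the first objective response to the first of disease progression".
- Section 9.3, PFS: "the interval between the first treatment day to the first sign of disease progression or death".

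The progression criteria in Section 9.1.3 do not include death, so death cannot enter DoR through the meaning of progression. Section 11.2.2 says that "Kaplan-Meier survival analysis will be used to assess DoR, PFS, and OS, in the entire cohort", with 95% confidence intervals for medians and proportions of all three. No section gives a censoring rule for DoR, a competing-risk method, or a second DoR definition that includes death.

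Section 5.2 lists death separately from progression among the reasons for umbralisib to end: "until disease progression, discontinuation due to toxicity, subject death, subject withdrawal of consent, or investigator withdrawal".

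**The concern.** A Kaplan-Meier analysis with progression as the only event has one default treatment for a responder who dies first: censoring at death. That treats the patient as someone who could still have been observed to progress later. The same death in the same patient is an event for PFS. The two endpoints would then describe the same follow-up by different rules, and the report would not show it.

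At stake is how the DoR median and proportions are read. A reader who takes DoR as time alive and in response would see a figure that is too favourable whenever a responder dies without progression. The primary response rate, the sample size and all decisions are unaffected.

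**Working it through.** **Is there a figure to reproduce?** Not for DoR: the plan states no DoR median, event count or death rate. The response-rate inputs were checked instead. Clopper-Pearson with n = 12 gives 24.96% to 82.54% at 55% and 14.06% to 70.94% at 40%, which agrees with the intervals in Section 11.2.1.

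**Direction.** In both versions a patient who dies leaves the risk set at the same time, so the numbers at risk agree. Counting the death multiplies the curve by (1 − 1/number at risk) at that time; censoring leaves this factor out. The factor is below 1, so the progression-only curve is never lower.

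**Expected responders** (Section 11.1 rates, 12 per cohort): A 12 × 0.55 = 6.6; B 12 × 0.40 = 4.8; together 11.4. The illustration uses 7, 5 and 11. Cohort and pooled views are both shown because Section 11.2.2 refers to the entire cohort, while Section 11.1 says "Each cohort will be evaluated independently of each other". One death is 1/11 = 9.1%, 1/7 = 14.3% or 1/5 = 20.0% of responders.

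**One death without progression at rank k, all other times being progressions.** Let m be the median rank when the death counts. Just after the m-th time:

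- death counted: S = (n − m)/n
- death censored, k ≤ m: S = (n − m)/n × (n − k + 1)/(n − k)

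| Responders | m | S, death counted | S, death censored, k = 1 to m |
|---|---|---|---|
| 11 (pooled) | 6 | 5/11 = 0.455 | 0.500, 0.505, 0.511, 0.519, 0.530, 0.545 |
| 7 (A) | 4 | 3/7 = 0.429 | 0.500, 0.514, 0.536, 0.571 |
| 5 (B) | 3 | 2/5 = 0.400 | 0.500, 0.533, 0.600 |

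The median moves from the 6th to the 7th time for k = 2 to 6 (pooled), from the 4th to the 5th for k = 2 to 4 (A), and from the 3rd to the 4th for k = 2 to 3 (B). At k = 1, S is exactly 0.500 and the result depends on whether the median rule is S ≤ 0.5 or S < 0.5. For k > m neither S at m nor the median changes.

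**Against sampling error.** Order-statistic intervals for the median with all times observed:

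- n = 11, 2nd to 10th time: 1 − 2 × 12/2048 = 98.8% coverage
- n = 7, 1st to 7th: 1 − 2/128 = 98.4%
- n = 5, 1st to 5th: 1 − 2/32 = 93.8%

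A shift of one rank is well inside these.

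**With other censoring (hypothetical data).** Take 11 responders with times 3, 5, 6, 8, 10, 12, 14, 16, 18, 20 and 22 months; progressions at 3, 6, 10 and 14; deaths without progression at 5 and 12; the rest still in response.

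- Deaths censored: 10/11 × 8/9 × 6/7 × 4/5 = 0.554, median not reached.
- Deaths counted: 10/11 × 9/10 × 8/9 × 6/7 × 5/6 × 4/5 = 0.416, median 14 months.

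**Chance of at least one such death among 11 responders**, for an assumed risk p per responder: 1 − (1 − p)^11 = 43% at p = 5%, 69% at 10%, 91% at 20%.

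**The case against.** The strongest reply is that this is a drafting slip, not a choice. The sentence in Section 9.2 is visibly incomplete, and its wording could have lost a second event or simply the word that Section 9.3 has in the same place. The plan never says that such a death is censored; that step is inferred. This stands as far as intent goes: the text does not show whether leaving out death was meant. But an analyst must program something, the only end event named is progression, and ordinary Kaplan-Meier then censors the death.

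Second, the list in Section 5.2 is generic and covers non-responders too. That is fair. It shows that the plan recognises death apart from progression, and says nothing about how often it happens in responders.

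Third, the effect is small and conditional. With one death and no other censoring, the median moves, whatever the tie convention, for only 5 of 11, 3 of 7 or 2 of 5 possible ranks, and always within sampling error. This also stands, and it limits the weight of the point. It does not remove it: in a descriptive study the reported estimate is the result, and its direction of error is known.

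Fourth, a progression-only DoR can be coherent if it is labelled as such and death is handled as a competing event. True, but the plan does neither. Finally, adding death leaves open how to treat a death after new CLL therapy. That is equally unaddressed for PFS, so it is no reason to keep the two definitions apart.

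**Conclusion.** The concern holds. As written, Section 9.2 with Section 11.2.2 leads to a DoR estimate that is equal to or higher than one using the PFS end events. The size depends on deaths without progression among roughly 11 responders, a number the documents do not give. It is zero with none. With one and no other censoring, the curve just after the median time rises by at most 9.1 percentage points pooled (54.5 − 45.5, from unrounded values), 14.3 in cohort A (57.1 − 42.9, likewise) or 20.0 in cohort B (60.0 − 40.0), and the median by at most one ordered time. With heavier censoring and two deaths, the hypothetical example changes a 14-month median to not reached. These figures rest on the plan's assumed response rates and on invented event orders. No trial conclusion changes; the definition should be corrected before analysis so that the reported DoR has a clear meaning.

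**What to change.** Complete the sentence in Section 9.2: DoR runs from first documented CR or PR to first documented progression or death from any cause, matching Section 9.3. If a progression-only measure was intended, say so, name it accordingly and analyse it by cumulative incidence with death as a competing event. In either case it is worth stating, for DoR and PFS alike, how patients without an event and those who start new CLL therapy are censored.

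The cost is small. No new data are needed, because subjects who stop therapy, other than by withdrawing consent, "will be followed for overall survival for up to 5 years". The downside is that the reported DoR may be slightly shorter.

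A separate editorial point, with no effect size claimed: Section 5.5 says that subjects who stop drug without progression "will be followed for progression free survival and survival every 3 months until documentation of disease progression, death" or new CLL therapy, but the next paragraph says that their visits "will continue for 3 months after study drug discontinuation" and yet lists 12-monthly CT. This is probably a slip. The Table 1 follow-up column and footnote e point to ongoing follow-up, while the asterisk footnote names only subjects stopping for toxicity. These passages should be reconciled.

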9.3. Progression-Free Survival

Progression-free survival is defined as the interval between the first treatment day to the first sign of disease progression or death.

9.4. Overall Survival

Overall survival duration is defined as the interval between the first treatment day to death.

10. Data Reporting / Regulatory Considerations

10.1 Data Collection

The data collection plan for this study is to utilize REDCap to capture all treatment, toxicity, efficacy, and adverse event data for all enrolled patients. REDCap (Research Electronic Data Capture) is a free data management software system that is fully supported by the Weill-Cornell Medical Center CTSC. It is a tool for the creation of customized, secure data management systems that include Web-based data-entry forms, reporting tools, and a full array of security features including user and group based privileges, authentication using institution LDAP system, with a full audit trail of data manipulation and export procedures. REDCap is maintained on CTSC-owned servers that are backed up nightly and support encrypted (SSL-

based) connections. Nationally, the software is developed, enhanced and supported through a multi-institutional consortium led by the Vanderbilt University CTSA.

10.2 Regulatory Considerations

All protocol amendments and consent form modifications will be made by the Principal Investigator. TG Therapeutics will have the opportunity to review and approve the changes prior to submission of these changes to the local IRB and distribution to participating sites.

11. Statistical Considerations

11.1 Study Design/Endpoints

In this single center Phase II study we will evaluate the efficacy and safety of umbralisib and ublituximab (U2) as salvage in patients with CLL who have progressed either on a BTK inhibitor or BCL-2 inhibitor. The study will enroll in two parallel cohorts and subjects will be assigned to cohorts based on the previous novel agent containing regimen regardless of how the novel agents were sequenced, **Cohort A** will consist of patients who progress on BTKi containing regimens and **Cohort B** will consist of patients who progress on BCL-2 containing regimens. Subjects who progress on a regimen containing both a BTKi and a BCL-2 inhibitor, will be enrolled in cohort B. Each cohort will be evaluated independently of each other.

Currently available retrospective evidence demonstrates an ORR of ~35-40% when idelalisib is used as first salvage after ibrutinib failure [11]. Given umbralisib's unique molecular properties and combination therapy with ublituximab, we hypothesize a response rate of 55% using U2 as first salvage. Salvage rates with novel agents after venetoclax failure in subjects considered double refractory are unknown. We anticipate close to 90% of patients enrolled in cohort B will have double refractory disease and represent a high risk group. Given these limitations, we anticipate a response rate of 40% in this group based off the efficacy seen with idelalisib after ibrutinib failure.

Because this is a pilot study, no formal sample size/power calculation is required. Given the anticipated different patient populations in each cohort, no cross cohort comparisons will be performed.

